#### 6.8 Treatment Compliance

Patients will complete drug administration diaries to track compliance with the recommended dosing schedule. These diaries will also capture the onset of AEs in relationship to the day of drug administration. The diaries will be returned to the Investigator at the subsequent visit.

#### 6.9 Pregnancy

The occurrence of pregnancy in a female subject or female partner of a male subject will be reported and recorded on the CRFs. Pregnancy will be handled as per usual clinical care. If interferon therapy is interrupted due to the pregnancy, this should be recorded on the CRFs.

Page 21

#### **Safety Monitoring** 7

#### 7.1 **Adverse Events**

An adverse event is the appearance or worsening of any undesirable sign, symptom, or medical condition occurring after starting the treatment even if the event is not considered to be related to the treatment. Treatment includes the investigational drug under evaluation and the comparator drug or placebo that is given during any phase of the study. Medical conditions/diseases present before starting treatment are only considered AEs if they worsen after starting treatment. Abnormal laboratory values or test results constitute AEs only if they induce clinical signs or symptoms, are considered clinically significant, or require therapy.

The occurrence of AEs should be sought by non-directive questioning of the patient at each visit during the study. Adverse events also may be detected when they are volunteered by the patient during or between visits or through physical examination, laboratory test, or other assessments. All Grade 3 or 4 AEs and all SAEs regardless of grade, must be recorded on the AE CRF with the following information:

- 1. the severity grade (3 or 4 AEs and all SAEs regardless of grade)
- 2. its relationship to HDI or PEG IFN therapy (suspected/not suspected)
- 3. its duration (start and end dates or if continuing at final exam)

All adverse events should be treated appropriately. Treatment may include one or more of the following: no action taken (ie, further observation only); treatment dosage adjusted/temporarily interrupted; treatment permanently discontinued due to this adverse event; concomitant medication given; non-drug therapy given; patient hospitalized/patient's hospitalization prolonged. The action taken to treat the adverse event should be recorded on the AE CRF.

Once an adverse event is detected, it should be followed until its resolution or until it is judged to be permanent, and assessment should be made at each visit (or more frequently, if necessary) of any changes in severity, the suspected relationship to the treatment, the interventions required to treat it, and the outcome.

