#### **Interferon Alfa**

The use of high-dose interferon (HDI) as adjuvant therapy following surgical resection of high-risk melanoma began in the early 1990s. The Eastern Cooperative Oncology Group (ECOG) 1684 trial examined the efficacy of 1-year HDI in patients with stage IIb-III melanoma (Kirkwood 1996). Patients were randomly assigned to receive HDI at a schedule of 20 MU/m^2/day intravenously (IV) for 5 consecutive days for 4 weeks (induction) followed by 10 MU/m^2/day subcutaneously (SC) 3 times per week (maintenance) for 48 weeks or observation. HDI was shown in the first analysis to significantly increase median relapse-free survival (RFS) (1.7 years versus 1 year; p=0.0023) and to prolong median overall survival (OS) (3.8 years versus 2.8 years; p=0.0237). In a follow-up analysis, the difference in OS was no longer statistically significant; however, the improvement in RFS persisted. The prolongation of RFS was only clearly shown for patients with stage III disease; however, there were too few stage II patients in the trial to draw a meaningful conclusion regarding its benefit in this patient population. Similar results to those obtained in ECOG trial 1684 were seen in subsequent trials in high-risk patients including Intergroup trials E1690 and E1694. The results of these trials have established the treatment schedule from E1684 as a standard of care for the adjuvant therapy of high-risk melanoma. A subsequent trial (E1697) was also performed to compare 1 month of induction therapy to observation for patients with stage IIa

disease. Accrual to this trial was halted when a planned interim analysis showed no difference in RFS or OS.

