#### 2.2 Secondary Objectives

- To compare perceptions of chemotherapy for patients on standard HDI versus PEG IFN using the Chemotherapy Convenience and Satisfaction Questionnaire (CCSQ) and to evaluate the treatment-related side effects that may impact the patient's HRQOL using the Functional Assessment of Cancer Therapy of Biologic Response Modifier (FACT-BRM)
- To assess the frequency of Grade 3 and 4 toxicities, according to the National Cancer Institute (NCI) Common Toxicity Criteria for Adverse Events-CTCAE, Version 4.0
- To examine the reasons for patients' choice of treatment with PEG IFN versus HDI
- To assess Health Resource Utilization on both arms of the study

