Item CS13, which rates the chemotherapy regimen overall, will be presented descriptively for the two treatment groups at the end of the study (i.e., 12 months). No inferential analyses will be conducted for this item.

- To evaluate the treatment-related side effects that may impact the patient's health-related QoL (HRQOL) using the Functional Assessment of Cancer Therapy of Biologic Response Modifier (FACT-BRM), with a 30% between-group difference in scores deemed clinically relevant, a mixed randomized-repeated measures ANOVA will be conducted for all items as a summation score, similar to the analysis plan described for CCSQ items CS1 GP5 (page 23, second bullet point). Separate subscales will be presented descriptively for the two treatment groups.
- The frequency of Grade 3 and 4 toxicities, according to the National Cancer Institute (NCI) Common Toxicity Criteria for Adverse Events (CTCAE) for patients on standard HDI versus PEG IFN, will be presented descriptively for the two treatment groups at 2 weeks, 3 months, 6 months and 12 months. No inferential analyses will be conducted for this outcome.
- Patients' reasons for their choice of treatment with HDI versus PEG IFN, for those cases in which patients are presented with a choice of either treatment option, will be reported descriptively at the study's conclusion (i.e., 12 months). No inferential analyses will be conducted for this outcome.

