#### 9.2 Safety

The only adverse events that will be counted will be treatment-emergent Grade 3 and 4 AEs and treatment-emergent SAEs regardless of grade. These events are those that started after the start of that treatment period, or were present prior to the start of the treatment period but increased in severity, or changed from being not suspected to being suspected to be due to treatment.

Treatment-emergent adverse events will be summarized separately for each treatment group and by body system and preferred term. Any other information collected (eg, severity or relatedness to treatment) will be listed as appropriate.

Laboratory data will be summarized by presenting summary statistics of raw data and change from baseline values (means, medians, standard deviations, ranges) will be provided.

Data from other tests will be listed, notable values will be flagged, and any other information collected will be listed as appropriate. Any statistical tests performed to explore the data will be used only to highlight any interesting comparisons that may warrant further consideration.

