- Treatment-related side effects that may impact the patient's health-related QoL (HRQOL) using the Functional Assessment of Cancer Therapy of Biologic Response Modifier (FACT BRM), with a 30% between-group difference in scores deemed clinically relevant. Time points of comparison were baseline/week 1, week 3, week 13, week 25, and week 50.

- The frequency of Grade 3 and 4 adverse events (AEs), according to the National Cancer Institute (NCI) Common Toxicity Criteria for Adverse Events (CTCAE) for patients on standard HDI versus PEG IFN, and the frequency of severe adverse events (SAEs), regardless of grade.
- Patients' reasons for their choice of treatment with HDI versus PEG IFN at the study's conclusion, for those cases in which patients were presented with a choice of either treatment option.

All analyses were conducted using IBM SPSS Statistics for Windows, Version 25.0 (Armonk, NY: IBM Corp.), with $p < .05$ denoting statistical significance.

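### Grade 3/4 'toxicity' by arm is tabulated as all-cause events, with no suspected-only total and no separate row for melanoma recurrence

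*Protocol*

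**What the plan says.** Protocol Section 2.2 sets the objective: "To assess the frequency of Grade 3 and 4 toxicities". The secondary outcomes in Section 9 keep the word toxicities and plan a descriptive comparison of the two groups, without inferential tests.

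Section 7.1 defines an adverse event as the "appearance or worsening of any undesirable sign, symptom, or medical condition occurring after starting the treatment". Causality plays no part in this definition, so unrelated events qualify. It limits when laboratory values and pre-existing conditions count. It says nothing about recurrence of the melanoma. For each recorded event the CRF must give "its relationship to HDI or PEG IFN therapy (suspected/not suspected").

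Section 9.2 then says "The only adverse events that will be counted will be treatment-emergent Grade 3 and 4 AEs", together with treatment-emergent SAEs of any grade. No filter on relationship is applied. Events are summarised by arm, body system and preferred term; relatedness is only to be listed. The SAP's secondary outcomes refer to adverse events rather than toxicities, and add SAEs of any grade. The SAP mentions neither relatedness nor recurrence.

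**The concern.** The objective asks how much severe toxicity each interferon causes. The planned totals answer a wider question: how many severe or serious events of any cause occurred in each arm. Patients enter after resection, so a recurrence is a condition that appears after treatment starts. If it is Grade 3/4 or serious, it meets the definition and is counted.

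This matters for the comparison because patients and physicians choose the arm (Protocol Sections 3 and 5.2), the inclusion criteria set no stage limit (Section 4.1), and Section 1.1 itself ties recurrence risk to pathologic features. Stage is not named among the baseline data in Section 6.1, and no adjustment for it is planned. If one arm held more advanced disease, part of its extra relapse could appear in its toxicity total. The study is meant to show whether a larger trial is warranted, so the toxicity contrast should be readable as such.

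**Working it through.** **No plan figure to reproduce.** Neither document gives an expected Grade 3/4 rate, a power statement or an event count for this outcome. The check is a reading of the text followed by an illustration of size.

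**Path of a relapse through the plan**
1. It appears after treatment starts and is not excepted, so it is an adverse event (Section 7.1).
2. If it is Grade 3/4 or serious, it is recorded, up to the last treatment day (Tables 2 and 3, footnote h).
3. It is counted in its arm whatever its recorded relationship (Section 9.2).
4. It is reported under an outcome that the protocol calls toxicities.

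**Inputs for the illustration**
- Median relapse-free survival on HDI of 1.7 years, from a cited trial in stage IIb-III disease (Protocol Section 1.1). This is used only to set a range.
- A 5-year median for a lower-risk group: assumed.
- True Grade 3/4 toxicity t = 30%, the same in both arms: assumed.
- Share g of relapses recorded as Grade 3/4 or SAE, 25% to 75%: assumed.
- Relapse and toxicity independent, and every patient observed for a full year: assumed.

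**One-year relapse**, exponential: r = 1 − 0.5^(1/median).
- 1.7 years: 1 − 0.5^(1/1.7) = 33.5%
- 5 years: 1 − 0.5^(1/5) = 12.9%, taken as 13%

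**Reported frequency** = 1 − (1 − t)(1 − r·g).

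| r | g = 25% | g = 75% |
|---|---|---|
| 13% | 1 − 0.70 × 0.9675 = 32.3% | 1 − 0.70 × 0.9025 = 36.8% |
| 33.5% | 1 − 0.70 × 0.91625 = 35.9% | 1 − 0.70 × 0.74875 = 47.6% |
| Spurious difference | 3.6 points | 10.8 points |

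**Sensitivity.** The spurious difference is (1 − t) × g × (difference in r).
- Equal relapse risk: 0 points, although both totals are raised.
- 13% vs 33.5%, t = 50%: 0.50 × 0.205 × g = 2.6 to 7.7 points. With t = 70%: 0.30 × 0.205 × g = 1.5 to 4.6 points.
- 33.5% vs 50% (50% being the conversion of the 1-year median on observation in the same cited trial), t from 30% to 70%, g from 10% to 100%: 0.5 to 11.6 points.
- 15% vs 50%, a deliberately extreme assumed imbalance, with t = 30% and g = 100%: 0.70 × 0.35 = 24.5 points.

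**Scale.** With 100 patients at the 60:40 cap and proportions near 50%, the 95% half-width of a difference is 1.96 × √(0.25/60 + 0.25/40) = 20 points. Of the scenarios above, only the last exceeds it.

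**After the fix.** With recurrence taken out of the total, the spurious difference in this model is 0. In the suspected-only version it is also 0, provided relapses are marked as not suspected.

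**The case against.** A reader might infer that the Section 7.1 definition is itself at fault. The documents do not support that. A definition that ignores causality, paired with a relationship field for every recorded event, is sound; what is missing is a planned use of that field in Section 9.2 and the SAP.

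A reader might also infer that relapses would be invisible, or that a suspected-only comparison is out of reach. Neither follows. Section 8.3 codes events in MedDRA and Section 9.2 summarises them by arm and preferred term, so a recurrence entered as such would usually have its own line. It is lost only in a pooled total, or where a site recorded a symptom or procedure instead. The relationship data exist, so a suspected-only count can be made at any time.

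Nor does every unrelated event enter the count. Only Grade 3/4 events and SAEs up to the last treatment day do. Section 5.4.1 ends study procedures at permanent discontinuation, and Section 1.1 says only that over 60% of patients complete a year of HDI. A full year of relapse therefore overstates the window for many patients.

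The label mismatch is also partly resolved, since the SAP itself says adverse events. The comparison is descriptive, in a pilot, and sampling error usually exceeds the illustrated bias. How sites were told to record recurrence may be covered in the multi-site procedures manual, which is not among the documents.

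All of this stands, and it makes the point a small one. It does not supply the missing total: the plan still contains no summary figure that answers the toxicity objective, and an interval for sampling error does not reveal a systematic difference.

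**Conclusion.** The point holds as a gap in tabulation. The stated outcome is toxicity, the planned totals are all-cause, and a Grade 3/4 or serious relapse on treatment enters them without separation.

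It would be too strong to say that an arm with more advanced disease will look more toxic. That needs a difference in relapse risk between arms, which the documents neither report nor rule out, and it needs relapses to be recorded as Grade 3/4 or serious. With equal relapse risk the spurious difference is zero. The 4 to 11 points rest on assumed relapse of 13% versus 33.5%, assumed toxicity of 30% and an assumed recording share of 25% to 75%. Within those assumptions they are upper-range, because collection stops with treatment, and they lie inside a sampling half-width of about 20 points. This is a cheap improvement to reporting and does not by itself undermine the safety results.

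**What to change.** Leave the Section 7.1 definition as it is. The SAP, revised in July 2023, describes its analyses as already done, so a new definition or CRF field could not alter what was collected.

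In Section 9.2 and the SAP:
- Tabulate Grade 3/4 AEs and SAEs by arm in two versions, all-cause and suspected only, using the relationship field already on the CRF.
- Show melanoma recurrence, and admissions or procedures solely for it, in a separate row identified by MedDRA term and excluded from the toxicity total.

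The cost is one extra table from existing data. Suspected is an unblinded judgement, which is why both versions should be shown. Recurrences entered only as a symptom or procedure may escape identification by term, and a footnote should say so.

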#### 8 **Data Review and Database Management**

#### 8.1 **Site Monitoring**

Before study initiation at any sub-sites, a study representative will review the protocol and CRFs with the investigators and their staff, and protocol training will be documented

The investigator must maintain source documents for each patient in the study, consisting of case and visit notes (hospital or clinic medical records) containing demographic and medical information, laboratory data, and the results of any other tests or assessments. All information on CRFs must be traceable to these source documents in the patient's file. Data not requiring a separate written record will be defined before study start and will be recorded directly on the CRFs. The investigator must also keep the original informed consent form signed by the patient (a signed copy is given to the patient).

All multi-site procedures outlined in the multi-site procedures manual must be followed. No information in source documents about the identity of the patients will be disclosed.

#### 8.2 Data Collection

Designated investigator staff must enter the information required by the protocol onto the paper CRFs, and copies of the interferon preference questionnaire, treatment perceptions, HRQOL evaluations and the drug administration diaries will be sent to the coordinating center as outlined in the multi-site procedures manual.

#### 8.3 Database Management and Quality Control

Data from the interferon preference questionnaire, treatment perception questionnaire,HRQOL evaluations and drug administration diaries will be reviewed by the coordinating center staff following their own internal standard operating procedures.

Errors or omissions on paper CRFs will generate queries that will be returned to the investigational site for resolution. Quality control audits will be completed as outlined in the multi-site procedures manual, and prior to finalizing data.

Medical history/current medical conditions and adverse events will be coded using the Medical Dictionary for Regulatory Activities (MedDRA) terminology.

### 9 Data Analysis

This is an observational pilot study with no formal sample size calculation based on a previously established effect size. For both primary and secondary outcomes, descriptive data will be presented (i.e., means and standard deviations or medians and interquartile ranges for interval and ordinal data as appropriate; frequencies and percentages for nominal/categorical data). Missing data will not be imputed due to the study's exploratory nature; however, all missing data points will be recorded and assessed for possible response patterns.

Selected inferential analyses will be conducted for exploratory purposes using estimated clinically important between-group differences. The study authors will seek to maintain at least a 60:40 between-group ratio to guard against unequal variance.

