#### 5.4.1 Treatment Discontinuation and Premature Patient Withdrawal

The investigator may at any time determine that a patient should no longer receive treatment with HDI or PEG IFN for reasons related to patient safety or for other reasons. If a patient's treatment with interferon is permanently discontinued, all study procedures will also be discontinued. All data obtained prior to treatment discontinuation will be included in the analysis set.

Patients may voluntarily withdraw from the study for any reason at any time. They may be considered withdrawn if they state an intention to withdraw, or fail to return for visits, or become lost to follow up for any other reason.

If premature withdrawal occurs for any reason, the investigator must determine the primary reason for a patient's premature withdrawal from the study and record this information on the Study Completion case report form (CRF). Patients who are prematurely withdrawn from the study will not be replaced.

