#### Primary outcome

• To compare compliance with HDI and PEG IFN (percentage of doses taken as recorded in patient diaries), with a 30% between-group difference deemed clinically relevant, a mixed randomized-repeated measures analysis of variance (ANOVA) will be conducted with treatment group (HDI versus PEG IFN) as the randomized (between-group) factor and treatment period time as the repeated measures (withingroup) factor. For the repeated measures factor of time, given the different induction phases for the two regimens (i.e., approximately 4 weeks for HDI versus 8 weeks for PEG IFN), the ANOVA will capture outcomes at baseline, 2 weeks, 3 months, 6

months and 12 months, with inclusion of the latter outcome dependent on the amount of missing data.

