Data Analysis -REVISED JULY 2023

Due to the study's pilot study design, sample size was not calculated formally. For both primary and secondary outcomes, descriptive data are presented (i.e., medians and ranges for continuous data, frequencies and percentages for categorical data).

Although the original data plan called for exploratory mixed randomized-repeated measures analysis of variance (ANOVA) to be conducted for the primary and two secondary outcomes, the pattern of missing data across patients at the designated time points was too prevalent (and appeared not to be missing at random) to ensure robust ANOVA results. Therefore, we reported separate non-parametric statistical outcomes when deemed feasible (i.e., adequate and balanced subgroup sample sizes) in an attempt to obtain as much information as possible about data trends and patterns. Because we were unable to capture within-subject correlations over time, as well as the treatment group*time interaction, our results should be interpreted accordingly.

The primary outcome was compliance with HDI and PEG IFN (i.e., percentage of doses taken based on total doses required over 53 weeks, as recorded in patient diaries), with a difference of 30% between groups deemed clinically relevant. We reported frequencies and percentages per week and an overall percentage of doses taken at the end of 53 weeks, with statistical analysis of this outcome.

Secondary outcomes were as follows (with different time points reported depending on the highest outcome frequencies):

- Comparison of the convenience and satisfaction with chemotherapy for patients on standard HDI versus PEG IFN using a chemotherapy convenience and satisfaction questionnaire (CCSQ), summation of items CS1 – GP5, with a 30% between-group difference deemed clinically relevant. Time points of comparison were baseline/week 1, week 3, week 13, week 25, and week 50.
- Item GF7, which assesses contentment with current quality of life, at baseline/week 1, week 3, week 13, week 25, and week 49.
- Item CS10, which assesses satisfaction with current results of chemotherapy, at week 1, week 3, week 13, week 25, week 37, and week 45.
- Items CS11 and CS12, which measure recommendation/choice of chemotherapy regimen, at week 1, week 3, week 13, week 25, week 37, and week 45.
- Item CS13, which rates the chemotherapy regimen overall, at week 1, week 3, week 13, week 25, week 37, and week 45.

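### CCSQ and FACT-BRM: week-by-week comparisons replace the repeated-measures ANOVA, although a mixed model on all observed scores would need a weaker missing-data assumption

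*Protocol*

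**What the plan says.** **Protocol, Section 9 (Data Analysis).** "Missing data will not be imputed", a choice put down to the exploratory purpose of the study, although missing points are to be recorded and examined for patterns. Under Primary outcome, treatment group enters the ANOVA "as the randomized (between-group) factor and treatment period time as the repeated measures" factor, at baseline, 2 weeks and 3, 6 and 12 months. Month 12 comes "with inclusion of the latter outcome dependent on the amount of missing data". The same design is specified for the CCSQ sum of CS1 to GP5 and for the FACT-BRM total.

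**Protocol, Section 5.4.1.** If interferon is "permanently discontinued, all study procedures will also be discontinued". Data gathered up to that point stay in the analysis set. The synopsis (End-of-Study Assessment), however, asks every treated patient back within 21 days of stopping, for treatment-perception and HRQOL evaluations among other things.

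**Protocol, Section 1.1 (Toxicity and Quality of Life on Interferon Therapy).** HDI has a high discontinuation rate, with over 60% completing one year. PEG IFN side effects are described as similar but less intense.

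**SAP (revised July 2023).** The missing-data pattern was "too prevalent (and appeared not to be missing at random) to ensure robust ANOVA results". Separate non-parametric results are given where subgroup sizes were adequate and balanced, at time points picked by how much data they held. For CCSQ and FACT-BRM these are baseline/week 1 and weeks 3, 13, 25 and 50. The SAP adds a caution: "Because we were unable to capture within-subject correlations over time", or the group-by-time interaction, the results must be read with that in mind. The primary outcome becomes one overall percentage of doses over 53 weeks.

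**The concern.** The SAP gives up one method because of the missing-data mechanism and moves to another that is generally no safer against it. A comparison at week 25 or week 50 on whoever still has a score makes no use of what earlier scores say about the patients who have gone. If patients who feel worse stop treatment, and more of them stop in one arm, the later comparison sets one arm's tolerators against a less selected group. The arm with more toxicity-driven dropout then looks better than it is.

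The protocol makes this plausible. Section 5.4.1 ends study procedures when treatment ends, and Section 1.1 expects milder side effects with PEG IFN. At stake is how two secondary outcomes are read, at p < .05, in a pilot meant to inform whether a larger trial is warranted.

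**Working it through.** **1. Plan's own figure.** There is none to reproduce. The documents give no SD, power, per-visit missing rate or dropout by arm, so every input below that is not traced to a section is an assumption.

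**2. Cost of complete rows.** A classical repeated-measures ANOVA without imputation uses only patients observed at every analysed visit. Take 100 patients (Section 9.3) and 60% one-year completion (the HDI background figure in Section 1.1, assumed for both arms). Let m be further independent missingness per visit.
- Five visits: 100 × 0.60 × (1 − m)^5. This gives 60 patients at m = 0, and 46, 35 and 20 at m = 5%, 10% and 20%.
- Month 12 left out, with 80% assumed still on study at month 6: 100 × 0.80 × (1 − m)^4. This gives 80, 65, 53 and 33.

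Leaving out month 12 reduces the loss without removing it. Either way, partial records that Section 5.4.1 keeps in the analysis set would go unused.

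**3. Ranking of assumptions.** A per-week comparison in general needs missingness unrelated to outcome within arm. A likelihood-based mixed model lets missingness depend on scores already observed (missing at random, MAR). It uses every observed visit, so incomplete rows do not stop it estimating within-subject correlation or arm-by-visit. Neither approach is valid in general if missingness depends on the unseen score (missing not at random, MNAR).

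**4. Size, first simulation.** 60 versus 40 patients, five visits, no true difference, unit SD, AR(1) correlation 0.6, 4,000 runs per row. Dropout is monotone, with logit of the dropout probability = −2.2 + s × score. The score is the previous one for MAR and the current one for MNAR. The per-week test is taken as Mann-Whitney; the model estimate is unstructured maximum likelihood.

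| Dropout | Last-visit bias (SD) | Mann-Whitney rejects | Complete-case bias (SD) | Complete-case test rejects | Likelihood bias (SD) |
|---|---|---|---|---|---|
| Unrelated to score (s = 0) | 0.00 | 4.8% | 0.00 | 5.6% | 0.00 |
| MAR, same in both arms (s = 1) | 0.00 | 4.8% | 0.00 | 5.0% | 0.00 |
| MAR, differing (s = 1.2 and 0.4) | 0.11 | 7.0% | 0.18 | 17.4% | 0.003 |
| MAR, one arm (s = 1.2 and 0) | 0.17 | 9.1% | 0.28 | 33.4% | 0.003 |
| MNAR, one arm (s = 1.2 and 0) | 0.28 | 17.5% | 0.27 | 33.3% | 0.20 |

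In the three unequal rows about 34 of 60 (56%) and 26 of 40 (65%) are retained. Only bias, not test size, was computed for the likelihood estimate.

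**5. Size, second simulation.** Same group sizes and visits, SD 22, correlation 0.65, stronger MAR dropout in HDI (46–52% retained versus 65–66%), 3,000 runs each. Last-visit bias was 5.3 to 9.1 points, that is 5.3/22 = 0.24 to 9.1/22 = 0.41 SD. The Mann-Whitney test rejected in 14.4% to 31.7% of runs. Likelihood bias was at most 0.02 points.

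**6. Scale.** CS1 to GP5 is 10 items scored 0 to 4 (Appendix 13.1), so the sum runs from 0 to 40 and its SD cannot exceed about 20. An SD of 22 therefore cannot describe the CCSQ sum, and the results should be read in SD units only.

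**The case against.** The case on the other side is substantial, and several stronger readings that a reader might infer do not hold.

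- **The ANOVA was abandoned.** True, so its complete-row problem matters mainly as a reason not to return to it. Listwise deletion is a property of the method and is not written in the protocol. Nor is the refusal to impute itself the fault, since a mixed model does not impute either.
- **The primary outcome.** One might infer that compliance is also tested visit by visit, or that its ANOVA has an undefined baseline level. The SAP makes compliance one 53-week percentage, so both readings are moot.
- **Complete-case loss.** Using (1 − q)^4 alone, 30% missing at each of four visits leaves 24%. That assumes independent misses. If patients simply drop out and stay out, 30% missing at the last visit leaves 70%.
- **The simulations favour the model.** Under MAR, near-zero likelihood bias follows from the assumption, while the SAP says the data appeared not to be MAR. In the MNAR row the gain is (0.28 − 0.20)/0.28, a little over a quarter. HDI retention of 46–56% is also below the protocol's figure of over 60%.
- **No bias is shown for this trial.** It needs outcome-related dropout that differs by arm. The documents make that plausible but do not report it. To say that per-week tests are valid only when data are missing completely at random is too strong, as the second row of the table shows.
- **The test is not named.** The SAP says non-parametric; Mann-Whitney is my assumption. It also limits testing to adequate, balanced subgroups and cautions the reader.
- **On-treatment description is a fair target.** The protocol wants to follow well-being during therapy, and CCSQ items concern treatment being received. This stands, and it is why the per-week summaries should stay.

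**Conclusion.** The point holds for the CCSQ sum and the FACT-BRM total only. The per-week comparisons need a stronger missing-data assumption, in general, than a mixed model on the same data. The SAP's remark about lost within-subject correlation and group-by-time is true of the ANOVA and of per-week tests, but not of every available method.

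The size is illustrative: about 0.1 to 0.4 SD of last-visit bias and about 7% to 32% false rejection under arm-dependent MAR dropout, against about zero bias for the model; 0.28 versus 0.20 SD under MNAR in one arm; none with the same mechanism in both arms and no true difference. A reader might infer that the mixed model cures the problem. It does not: it reduces bias without removing it if the data are MNAR, and it does nothing about patients having chosen their own treatment. Because the study is an exploratory, non-randomized pilot, this is a worthwhile improvement to the secondary analyses and does not invalidate the study.

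**What to change.** 1. Fit an exploratory mixed model for repeated measures to all observed CCSQ (CS1 to GP5) and FACT-BRM scores, with arm, visit, arm-by-visit and baseline score. Use an unstructured covariance, with a simpler structure named in advance if it does not converge.
2. Include any questionnaires completed at the end-of-study visit. Section 5.4.1 and the synopsis must be reconciled on whether assessments continue after discontinuation.
3. Add one delta-adjusted MNAR sensitivity analysis that shifts the unobserved scores of patients who stopped by a stated range of amounts, allowed to differ by arm. If it is run through imputation, state it as an exception to the no-imputation rule.
4. Keep the per-week medians and ranges, labelled as on-treatment description.
5. Label the new analyses post hoc and exploratory, since the SAP is written after the fact.

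Cost: reworded SAP text, one model per score and one sensitivity analysis, on data already collected; the mixed model is available in the software the SAP names. The downsides are a normal-error assumption for summed ordinal scores and possible convergence trouble at sparse visits.
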